7.5 INSTITUTIONAL BIOSAFETY COMMITTEE (IBC) REPORTING CRITERIA

7.5.1 Serious Adverse Event Reports to IBC

The Principal Investigator (or delegate) will notify IBC of any unexpected fatal or life-threatening experience associated with the use of ETBX vaccines as soon as possible but in no event later than 7 calendar days of initial receipt of the information. Serious adverse events that are unexpected and associated with the use of the ETBX vaccines, but are not fatal or life-threatening, must be reported to the NIH IBC as soon as possible, but not later than 15 calendar days after the investigator's initial receipt of the information. Adverse events may be reported by using the FDA Form 3500a.

7.5.2 Annual Reports to IBC

Within 60 days after the one-year anniversary of the date on which the IBC approved the initial protocol, and after each subsequent anniversary until the trial is completed, the Principal Investigator (or delegate) shall submit the information described below. Alternatively, IRB continuing review report can be sent to the IBC in lieu of a separate report. Please include the IBC protocol number on the report.

7.5.2.1 Clinical Trial Information

A brief summary of the status of the trial in progress or completed during the previous year. The summary is required to include the following information:

- the title and purpose of the trial
- clinical site
- the Principal Investigator
- clinical protocol identifiers;
- participant population (such as disease indication and general age group, e.g., adult or pediatric);

- the total number of participants planned for inclusion in the trial; the number entered into the trial to date whose participation in the trial was completed; and the number who dropped out of the trial with a brief description of the reasons
- the status of the trial, e.g., open to accrual of subjects, closed but data collection ongoing, or fully completed,
- if the trial has been completed, a brief description of any study results.

7.5.2.2 Progress Report and Data Analysis

Information obtained during the previous year's clinical and non-clinical investigations, including:

- a narrative or tabular summary showing the most frequent and most serious adverse experiences by body system
- a summary of all serious adverse events submitted during the past year
- a summary of serious adverse events that were expected or considered to have causes not associated with the use of the gene transfer product such as disease progression or concurrent medications
- if any deaths have occurred, the number of participants who died during participation in the investigation and causes of death
- a brief description of any information obtained that is pertinent to an understanding of the gene transfer product's actions, including, for example, information about dose-response, information from controlled trials, and information about bioavailability.

7.6 DATA AND SAFETY MONITORING PLAN

7.6.1 Principal Investigator/Research Team

The clinical research team will meet on a weekly basis when patients are being actively treated on the trial to discuss each patient, enrollment and data management issues. Decisions about dose level enrollment and dose escalation will be made based on the toxicity data from prior patients.

All data will be collected in a timely manner and reviewed by the principal investigator or associate investigator. Adverse events will be reported as required above. Any safety concerns, new information that might affect either the ethical and or scientific conduct of the trial, or protocol deviations will be immediately reported to the IRB using iRIS.

The principal investigator will review adverse event and response data on each patient to ensure safety and data accuracy. The principal investigator will personally conduct or supervise the investigation and provide appropriate delegation of responsibilities to other members of the research staff.

7.6.2 Sponsor Monitoring Plan

As a sponsor for clinical trials, FDA regulations require the CCR to maintain a monitoring program. The CCR's program allows for confirmation of: study data, specifically data that could affect the interpretation of primary study endpoints; adherence to the protocol, regulations, and SOPs; and human subjects protection. This is done through independent verification of study data with source documentation focusing on:

- Informed consent process
- Eligibility confirmation
- Drug administration and accountability
- Adverse events monitoring
- Response assessment.

The monitoring program also extends to multi-site research when the CCR is the coordinating center.

This trial will be monitored by personnel employed by an CCR contractor. Monitors are qualified by training and experience to monitor the progress of clinical trials. Personnel monitoring this study will not be affiliated in any way with the trial conduct.

7.6.3 Safety Monitoring Committee (SMC)

This protocol will require oversight from the Safety Monitoring Committee (SMC). Initial review will occur as soon as possible after the annual NCI-IRB continuing review date. Subsequently, each protocol will be reviewed as close to annually as the quarterly meeting schedule permits or more frequently as may be required by the SMC. For initial and subsequent reviews, protocols will not be reviewed if there is no accrual within the review period. Written outcome letters will be generated in response to the monitoring activities and submitted to the Principal investigator and Clinical Director or Deputy Clinical Director, CCR, NCI.

8 STATISTICAL METHODS

8.1 STATISTICAL HYPOTHESIS

This is a Phase I trial in subjects with advanced cancer. A combination ETBX-011, ETBX-051, ETBX-061 vaccine regimen using the same modified Adenovirus vector backbone, separately encoding three well-studied TAAs will be assessed. The vaccine will be tested at standard dose level, and a dose de-escalation (if required) design will be employed. The primary endpoint will be to determine the overall safety of combined ETBX-011/ETBX-061/ETBX-051 vaccine when administered SC to subjects with advanced solid tumors and establish a recommended phase 2 dose of vaccine. This will be reported when an MTD is determined (expected to be less than 1 year from trial start). A secondary endpoint will be to obtain preliminary data on ORR, DCR, duration of response, PFS, and OS in treated subjects (preliminary data will be assessed around two years following trial start). An exploratory hypothesis (objective) will be to evaluate the immunogenicity of the combined ETBX-011/ETBX-061/ETBX-051 vaccine.

8.2 SAMPLE SIZE DETERMINATION

Up to six patients will be enrolled in an initial dose level 1. If ≤ 1 of 6 patients experience a DLT, then the MTD will be declared, and initiation of the dose expansion phase will occur. If ≥ 2 of 6 experience DLT in the initial dose level 1, then dose de-escalation will occur. Up to six patients will be enrolled at the lower dose level (-1) (1×10^{11} VP). If ≤ 1 of 6 patients experience a DLT, then the maximum tolerated (MTD) will be declared at this dose, and initiation of the dose expansion phase will occur. If ≥ 2 of 6 (or ≥ 2 of the first 3) experience DLT in this second dose level -1, then an amendment may be written to further evaluate dose de-escalation. Once the MTD is identified, the dose expansion component will commence. An additional 4 subjects will be

enrolled at the MTD for a total of 10 subjects to gain additional safety data and exploratory data on vaccine immunogenicity.

We assume 16 patients will have screen failure. Therefore, up to 32 subjects will be enrolled in the study. Initial dose evaluation and or dose finding will require 6-12 subjects, followed by 4 additional subjects treated at a defined dose.

8.3 POPULATION FOR ANALYSES

Evaluable for toxicity: All patients will be evaluable for toxicity from the time of their first treatment with the combination ETBX-011, ETBX-051, ETBX-061 vaccine regimen.

Evaluable for objective response: Only those patients who have measurable disease present at baseline, have received at least one cycle of therapy, and have had their disease re-evaluated will be considered evaluable for response. These patients will have their response classified according to the definitions stated below. (Note: Patients who exhibit objective disease progression prior to the end of cycle 1 will also be considered evaluable.)

Evaluable Non-Target Disease Response: Patients who have lesions present at baseline that are evaluable but do not meet the definitions of measurable disease, have received at least one cycle of therapy, and have had their disease re-evaluated will be considered evaluable for non-target disease. The response assessment is based on the presence, absence, or unequivocal progression of the lesions.

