3.1.1 Dose Limiting Toxicity

For the purposes of dose escalation a dose limiting toxicity (DLT) is defined as:

- Any Grade 3 or greater toxicity that is possibly related to the vaccine and as defined by Common Terminology Criteria for Adverse Events (CTCAE) Version 5.0 with the exception of transient (≤ 24 hours) Grade 3 flu-like symptoms or fever, which is controlled with medical management or transient (≤ 24 hours) Grade 3 fatigue, skin reactions or rash, headache, nausea, emesis that resolves to Grade ≤ 1 or asymptomatic grade 3 amylase/lipase elevation. For purposes of dose escalation the DLT evaluation period will be for 3 weeks following the first dose of drug.

Subjects experiencing a DLT will be removed from protocol therapy.

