3.7.1 Criteria for removal from protocol therapy

- Completion of protocol therapy.
- Clinical or radiographic progression of disease Patients with serological progression alone will remain on treatment at the discretion of the PI.
- Unacceptable Toxicity as defined as any serious adverse event that is unexpected relative to the known safety profile of the investigational agents in the opinion of the investigator or as described in sections [3.1.1](#) and [3.3](#)
- Participant requests to be withdrawn from active therapy
- Investigator discretion
- Positive pregnancy test

Also see section [3.3](#)

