6.3 EFFICACY ASSESSMENTS

6.3.1 Antitumor Response

Tumor assessments will be done at week 6 and then every 8 weeks thereafter and may include the following evaluations: physical examination (with photograph and measurement of skin lesions, as applicable); cross-sectional imaging using computed tomography (CT) or magnetic resonance imaging (MRI) scan of the chest, abdomen, and pelvis (pelvis scan is optional unless known pelvic disease is present at baseline); nuclear bone scan for subjects with known/suspected bone lesions; and CT or MRI scan of the brain (only as clinically warranted based on symptoms/findings). The preferred method of disease assessment is CT with contrast. If CT with contrast is contraindicated, CT of the chest without contrast and MRI scan of the abdomen/pelvis with contrast is preferred. At baseline, tumor lesions will be selected and categorized as target (measurable disease) or non-target lesions (non-measurable disease).

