8.4.3.1 Objective Tumor Response and Disease Control Rate

The percentage of subjects that achieve an objective confirmed complete or partial overall tumor response using RECIST Version 1.1 will be evaluated by dose level and overall enrollment. If anti-tumor responses are observed, the 95% confidence interval of the response rate will be evaluated.

Disease control (confirmed response or SD lasting for at least 6 months) will be analyzed in a similar manner.

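### Section 8.3 lets treated subjects who stop before the first repeat scan drop out of the response denominator, and sections 8.1, 8.4.3 and 8.4.3.1 point to other denominators

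*Combined protocol and SAP*

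**What the plan says.** Section 8.3 restricts the objective-response analysis: only subjects with measurable disease at baseline who "have received at least one cycle of therapy, and have had their disease re-evaluated will be considered evaluable for response". One note widens this: "Patients who exhibit objective disease progression prior to the end of cycle 1 will also be considered evaluable". A parallel set covers subjects with evaluable but non-measurable lesions, and it has the same cycle and re-evaluation conditions. The length of a cycle is not defined; dosing is at weeks 0, 3 and 6 and then every 8 weeks. The only set in 8.3 that takes in all treated subjects is the one for toxicity.

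Section 8.4.3.1 says that the percentage with a confirmed response "will be evaluated by dose level and overall enrollment", and that disease control will be analysed similarly. It names no analysis set. Sections 8.1 and 8.4.3 introduce the same endpoints as preliminary data in treated subjects.

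Three other parts of the protocol determine who gets a repeat scan:

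- Section 3.1.1: "Subjects experiencing a DLT will be removed from protocol therapy", and "the DLT evaluation period will be for 3 weeks following the first dose of drug".
- Section 3.7.1 ends protocol therapy for "Clinical or radiographic progression of disease", so imaging is not required for removal.
- Section 6.3.1: "Tumor assessments will be done at week 6 and then every 8 weeks thereafter". The calendar in section 3.5 marks no tumor imaging at End of Treatment, and later follow-up is by telephone.

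**The concern.** A subject who was treated and stopped before the first scan because of toxicity, clinical decline or death did not achieve a response. Leaving that subject out makes the rate conditional on having tolerated treatment and survived to a re-evaluation. The same subject remains in the toxicity denominator at that dose level.

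Two things are at stake. First, any non-zero ORR from the 8.3 set is higher than the rate in treated subjects. Second, the rates are to be shown by dose level. If one level loses more subjects early than another, the comparison between levels partly reflects who was re-scanned.

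The plan also does not say which denominator applies, so the choice could be made after the responses are known.

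**Working it through.** **Step 1: the plan's own count.** Section 8.2 gives 6–12 subjects for dose finding, 4 for expansion and 16 screen failures. The maximum treated is 12 + 4 = 16, and 16 + 16 = 32, which matches the stated enrollment ceiling. Enrollment in 8.2 therefore includes screen failures. The plan states no ORR, response denominator or power.

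**Step 2: timing.** A DLT is identified within 3 weeks of the first dose under section 3.1.1 (section 8.4.4 says 1 week). Either window closes before the week 6 assessment, and no End of Treatment scan is marked. A subject removed at that point has no scheduled re-evaluation. The same holds for clinical progression, death or withdrawal before week 6. The exception in 8.3 covers objective progression only.

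**Step 3: is early stopping plausible?** In the earlier single-agent trial, all three 3-weekly doses were received by 28 of 32 subjects (section 1.2.6.3) or 28 of 34 (section 11.1.2). So 4/32 = 12.5% to 6/34 = 17.6% missed at least one dose. Missing a dose is not the same as missing a scan, so this supports plausibility only.

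**Step 4: size.** With r responders, n treated and d not re-scanned, the two rates are r/n (treated) and r/(n − d) (8.3 set), and their ratio is n/(n − d). I assume that everyone has measurable disease and that those who stop early are not re-scanned. The values of r and d are illustrative. Intervals are exact (Clopper-Pearson) 95%.

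| Setting | Treated, r/n | 8.3 set, r/(n − d) | Ratio |
|---|---|---|---|
| Level 1, n = 6, d = 2, r = 1 | 1/6 = 16.7% (0.4–64.1%) | 1/4 = 25.0% (0.6–80.6%) | 1.50 |
| Level 1, n = 6, d = 3, r = 1 | 1/6 = 16.7% (0.4–64.1%) | 1/3 = 33.3% (0.8–90.6%) | 2.00 |
| MTD, n = 10, d = 1, r = 1 | 1/10 = 10.0% (0.3–44.5%) | 1/9 = 11.1% (0.3–48.2%) | 1.11 |
| MTD, n = 10, d = 2, r = 2 | 2/10 = 20.0% (2.5–55.6%) | 2/8 = 25.0% (3.2–65.1%) | 1.25 |
| Overall, n = 16, d = 3, r = 2 | 2/16 = 12.5% (1.6–38.3%) | 2/13 = 15.4% (1.9–45.4%) | 1.23 |

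With r = 0 both rates are 0%.

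**Step 5: the competing denominators.** In the last row, a literal use of enrollment as counted in 8.2 gives 2/32 = 6.3%. The same two responders can therefore be reported as 15.4%, 12.5% or 6.3%.

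**Step 6: disease control.** If disease control used the same evaluable subjects, 4 cases among 10 treated with 2 not re-scanned would give 4/8 = 50% against 4/10 = 40%. This can matter even with no responses, because stable disease lasting at least 6 months counts as disease control.

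**Step 7: does the effect follow toxicity?** Two DLT removals among 6 give 6/4 = 1.50. One DLT plus three clinical deteriorations among 10 gives 10/6 = 1.67. The less toxic level then has the larger ratio.

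**The case against.** The strongest reply is that 8.4.3.1 never says it uses the 8.3 set. Sections 8.1 and 8.4.3 refer to treated subjects, and on that reading nothing is overstated. This stands as far as it goes: the documents show an unresolved denominator, not a certain bias. It does not remove the point, because 8.3 contains the plan's only stated response populations and its wording is exclusive.

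A reader might infer that a level failing on toxicity must lose at least two of its six subjects from the response denominator. The documents do not support that. Section 3.1.1 removes a DLT subject from therapy, and DLT is not among the off-study criteria in section 3.7.2. Section 6.3.1 does not limit assessments to subjects on treatment. A removed subject who is re-scanned could still qualify, depending on what one cycle means.

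A reader might also infer that ORR is inflated most where toxicity is worst. That holds only if DLT removals drive the missing scans, and step 7 shows the order can reverse.

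Other limits also stand. The responder and dropout counts are assumed. Section 2.1.1 admits non-measurable and resected disease, so real denominators may be smaller. The intervals are too wide for any of these rates to be informative alone. The note on early objective progression keeps some treatment failures in, and early deaths count in PFS and OS.

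**Conclusion.** The point holds in a limited form. If 8.3 is followed as written, treated subjects who stop before week 6 can drop out of the response denominator, and any non-zero ORR is then overstated relative to treated subjects. In the illustrations the ratio runs from 1.11 (one of ten not re-scanned) to 2.00 (three of six). Rates by dose level can be distorted when early removal is unequal, but the direction cannot be predicted from toxicity alone.

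These sizes rest on the assumptions that all subjects have measurable disease and that early stoppers have no later scan. With zero responses there is no effect on ORR. The endpoint is secondary and descriptive, and the DLT and MTD decisions use treated subjects and are unaffected. It should be corrected before the response data are analysed, but it does not threaten the primary objective.

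**What to change.** In sections 8.3 and 8.4.3.1:

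- **ORR:** make the main denominator all treated subjects with measurable disease at baseline, counting those with no post-baseline assessment as non-responders.
- **Disease control:** use all treated subjects with measurable or evaluable disease at baseline, handled in the same way.
- **Supplementary line:** keep the 8.3 re-evaluated set, and list the number omitted and the reason for each omission by dose level.
- **Terms:** define a cycle as a stated number of vaccination visits, and replace the reference to overall enrollment with the named set.

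This changes wording only. It needs no new data or visits and does not alter patient management. The cost is that the reported rates will be slightly lower.

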8.4 STATISTICAL ANALYSES

8.4.1 General Approach

Descriptive analyses of toxicity results and exploratory description of time-to-event and response based results. The planned analyses for each objective is described in the subsections below.

8.4.2 Analysis of Primary Efficacy Endpoints

Not applicable in this Phase 1 Study. The primary objective of evaluating safety is described in Section [8.4.4](#) below.

8.4.3 Analyses of Secondary Endpoint

Analyses of secondary endpoint to obtain preliminary data on objective response rate (ORR), disease control rate (DCR), duration of response, progression-free survival (PFS), and overall survival (OS) in treated subjects.

Since this is a Phase I trial, only preliminary data will be obtained for evidence of vaccine efficacy. Preliminary analyses of vaccine efficacy are described in the Sections [8.4.3.1](#) to [8.4.3.4](#) below.

8.4.3.1 Objective Tumor Response and Disease Control Rate

The percentage of subjects that achieve an objective confirmed complete or partial overall tumor response using RECIST Version 1.1 will be evaluated by dose level and overall enrollment. If anti-tumor responses are observed, the 95% confidence interval of the response rate will be evaluated.

Disease control (confirmed response or SD lasting for at least 6 months) will be analyzed in a similar manner.

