2 ELIGIBILITY ASSESSMENT AND ENROLLMENT

2.1 ELIGIBILITY CRITERIA

2.1.1 Inclusion Criteria

- 2.1.1.1 Age \geq 18 years (male and female).
- 2.1.1.2 Ability to understand and provide signed informed consent that fulfills Institutional Review Board (IRB)'s guidelines.
- 2.1.1.3 Subjects with cytologically or histologically confirmed locally advanced or metastatic solid tumor malignancy.
- 2.1.1.4 Subjects must have completed or had disease progression on at least one prior line of disease-appropriate therapy or not be candidates for therapy of proven efficacy for their disease.
- 2.1.1.5 Subjects may have measurable or nonmeasurable but evaluable disease as defined in section 6.3.1. Subjects with surgically resected locally advanced or metastatic disease at high risk of relapse are also eligible.
- 2.1.1.6 Eastern Cooperative Oncology Group (ECOG) performance status \leq 1 ([Appendices](#)
- 2.1.1.7 [Appendix A](#))
- 2.1.1.8 Subjects who have received prior CEA, MUC1, and/or Brachyury-targeted immunotherapy (vaccine) are eligible for this trial if this treatment was discontinued at least 4 weeks prior to enrollment.
- 2.1.1.9 Resolution of clinically significant side effects of prior chemotherapy, radiotherapy, immunotherapy or surgical procedures to NCI CTCAE Grade \leq 1 or grade \leq 2 for neuropathy.
- 2.1.1.10 Adequate hematologic function at screening, as follows:
 - 2.1.1.10.1 Absolute neutrophil count (ANC) \geq 1 x 10⁹/L
 - 2.1.1.10.2 Hemoglobin \geq 9 g/dL
 - 2.1.1.10.3 Platelets \geq 75,000/mcL.

2.1.1.11 Adequate renal and hepatic function at screening, as follows:

2.1.1.11.1 Serum creatinine ≤ 1.5 x upper limit of normal (ULN) OR creatinine clearance (CrCl) ≥ 40 mL/min (if using the Cockcroft-Gault formula below):

i. *Female* CrCl = [(140 - age in years) x weight in kg x 0.85] / [72 x serum creatinine in mg/dL]

ii. *Male* CrCl = [(140 - age in years) x weight in kg x 1.00] / [72 x serum creatinine in mg/dL]

2.1.1.11.2 Bilirubin ≤ 1.5 x ULN OR in subjects with Gilbert's syndrome, a total bilirubin ≤ 3.0 x ULN

2.1.1.11.3 Alanine aminotransferase (ALT) and aspartate aminotransferase (AST) ≤ 2.5 x ULN, unless liver metastases are present, then values must be ≤ 3 x ULN)

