6.3.5 Target Response

Percentage change in target lesion size will be evaluated by the following formulae:

1. When determining complete response or partial response:

$$[(\text{Post value} - \text{Baseline value})/\text{Baseline value}] \times 100$$

2. When determining progressive disease:

$$[(\text{Post value} - \text{Smallest value since treatment started})/(\text{Smallest value since treatment started})] \times 100$$

Target response will be classified according to the RECIST Version 1.1 Target Lesion Response Criteria in [Table 5](#).

Table 5: RECIST Target Response Criteria

Target Response Criteria	Definition
Complete Response (CR)	Disappearance of all target lesions. Any pathological lymph nodes (whether target or non-target) must have reduction in short axis to < 10 mm.
Partial Response (PR)	At least a 30% decrease in the sum of diameters of target lesions, taking as reference the baseline sum diameters.
Stable Disease (SD)	Neither sufficient shrinkage to qualify for PR nor sufficient increase to qualify for PD, taking as reference the smallest sum diameters while on study.
Progressive Disease (PD)	At least a 20% increase in the sum of diameters of target lesions, taking as reference the smallest sum diameters while on study (this includes the baseline sum if that is the smallest on study). In addition to the relative increase of 20%, the sum must also demonstrate an absolute increase of 5 mm. (Note: the appearance of one or more lesions is also considered progression).

Non-target response will be classified according to the RECIST Version 1.1 Non-Target Lesion Response Criteria in [Table 6](#).

Table 6: RECIST Non-Target Response Criteria

Non-Target Response Criteria	Definition
CR	Disappearance of all non-target lesions and normalization of tumor marker level. All lymph nodes must be non-pathological in size (< 10 mm short axis).
Non-CR / Non-PD	Persistence of one or more non-target lesion(s) and/or maintenance of tumor marker level above the normal limits.
PD	Unequivocal progression of existing non-target lesions. (Note: the appearance of one or more new lesions is also considered progression).

Overall response will be classified according to the RECIST Version 1.1 Overall Response Criteria in [Table 7](#).

Table 7: RECIST Overall Response Criteria

Target Lesions	Non-Target Lesions	New Lesions	Overall Response
CR	CR	No	CR
CR	Non-CR / Non-PD	No	PR
CR	Not Evaluated	No	PR
PR	Non-PD or not all evaluated	No	PR

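### The 95% confidence interval for the response rate is planned only if responses occur, with no method named, so no upper limit is planned for a zero-response result

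*Combined protocol and SAP*

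**What the plan says.** Section 8.4.3.1 plans the percentage of subjects with a confirmed complete or partial response, for each dose level and overall. It then adds: "If anti-tumor responses are observed, the 95% confidence interval of the response rate will be evaluated". DCR follows in the next sentence: "Disease control (confirmed response or SD lasting for at least 6 months) will be analyzed in a similar manner".

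This is the only confidence interval planned in the text supplied. Section 8.4.1 describes the response analyses as exploratory description. Section 8.4.3 says that only preliminary efficacy data will be obtained. Neither names an interval method or says what accompanies a zero count.

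The denominator is described in more than one way. Section 8.3 restricts the set used for ORR as follows: "Only those patients who have measurable disease present at baseline, have received at least one cycle of therapy, and have had their disease re-evaluated", with the note that "Patients who exhibit objective disease progression prior to the end of cycle 1 will also be considered evaluable". Section 8.4.3 refers to treated subjects, and 8.4.3.1 to overall enrollment.

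**The concern.** Whether uncertainty is reported should not depend on the result. Here the interval is dropped in the one case where the point estimate says least about precision: a bare 0% looks definite, while 0 out of 10 leaves a wide range of true rates open. The text is an explicit condition, so this is more than a detail left out.

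The missing method matters for the repair. If the condition were simply deleted and a normal-approximation interval then used, the result at zero would have no width. At stake is how a null result on a listed secondary endpoint would be read. No dose or safety decision is involved.

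**Working it through.** **Inputs.** From section 8.2: 6 to 12 subjects for dose evaluation, 4 more in expansion, 10 in total at the MTD, 16 assumed screen failures and up to 32 enrolled. From section 8.4.3.1: a 95% level, with sidedness not stated; two-sided is used here. The documents give no expected response rate, so true rates below are assumptions.

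**The plan's own counts.** 6 + 4 = 10 at the MTD. Treated overall: 6 + 4 = 10 up to 12 + 4 = 16. Enrolled: 16 + 16 = 32. These agree with section 8.2. The plan states no confidence limit to reproduce.

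**Upper limit at zero responses.** The exact (Clopper-Pearson) two-sided 95% upper limit for 0/n is 1 − 0.025^(1/n).

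| n | Setting | Upper limit |
|---|---|---|
| 6 | one dose level of six | 1 − 0.025^(1/6) = 45.9% |
| 10 | MTD total | 1 − 0.025^(1/10) = 30.8% |
| 16 | largest treated total | 1 − 0.025^(1/16) = 20.6% |

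The response denominator may be smaller, because section 2.1.1 allows that "Subjects may have measurable or nonmeasurable but evaluable disease as defined in section 6.3.1". If 8 of 10 were evaluable (assumed), the limit would be 1 − 0.025^(1/8) = 36.9%.

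**How likely zero is.** P(0 responses) = (1 − p)^n.

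| Assumed true ORR | n = 10 | n = 16 |
|---|---|---|
| 5% | 0.95^10 = 59.9% | 0.95^16 = 44.0% |
| 10% | 0.90^10 = 34.9% | 0.90^16 = 18.5% |
| 20% | 0.80^10 = 10.7% | 0.80^16 = 2.8% |

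Zero is more likely than not only if the true rate is below 1 − 0.5^(1/10) = 6.7% (n = 10) or 1 − 0.5^(1/16) = 4.2% (n = 16).

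**Why a method must be named.** The normal approximation is p ± 1.96 × √(p(1 − p)/n). At 0/10 it gives 0 ± 0, that is 0% to 0%. At 1/10 it gives 0.10 ± 1.96 × √(0.09/10) = 0.10 ± 0.186, that is −8.6% to 28.6%. The exact intervals are 0% to 30.8% and 0.3% to 44.5%. Wilson and Agresti-Coull upper limits at 0/10 are 27.8% and 32.1%.

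**Size of the denominator effect, for the optional addition.** Section 6.3.1 says "Tumor assessments will be done at week 6 and then every 8 weeks thereafter". A treated subject with measurable disease who stops before week 6 without objective progression falls outside the 8.3 response set. With one responder among 10 treated and 1, 2 or 3 not re-evaluated (assumed), ORR is 1/9 = 11.1%, 1/8 = 12.5% or 1/7 = 14.3%, against 1/10 = 10.0%. With zero responders the estimate stays at 0%, and only the upper limit changes with n.

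**The case against.** The strongest reply is that nothing depends on this interval. Section 8.4.2 says that primary efficacy analysis does not apply. Sections 8.4.1 and 8.4.3 make response results exploratory and preliminary, the sample size rests on the DLT rules, and 0/n already carries the information needed to compute a limit. All of this stands, and it keeps the point minor. It does not remove the result-dependent rule.

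It can also be said that no section proposes a normal approximation, and that Clopper-Pearson is partly a preference. That stands too: Wilson and Agresti-Coull give similar limits at 0/10. What matters is that one suitable method is named.

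A reader might infer three stronger things that the documents do not support.

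- **That the plan rules out an interval at zero.** It does not. It plans none, and the analyst remains free to add one.
- **That section 8.3 inflates ORR.** This follows only if the 8.3 set governs 8.4.3.1. Section 8.4.3 points to treated subjects, and the 8.3 note keeps early objective progressors in the set. The illustrated shift is also small against the intervals.
- **That disease control is undefined for subjects with only non-measurable disease.** Table 5 defines stable disease by the sum of target-lesion diameters. Table 6 gives non-target disease its own middle category: "Persistence of one or more non-target lesion(s) and/or maintenance of tumor marker level above the normal limits". Section 6.3.6 times stable disease against the smallest recorded measurements. The natural reading is that the non-target category alone is not stable disease. An explicit sentence on this, or on which 8.3 set DCR uses, would add detail; its absence is not an error.

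**Conclusion.** The point holds in a limited form. Followed as written, section 8.4.3.1 gives no planned upper limit when no response is seen, and no method for the interval when one is. DCR most naturally inherits the same rule. At zero, the unplanned upper limits are 45.9% (n = 6), 30.8% (n = 10) and 20.6% (n = 16).

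These limits rest on the exact two-sided method and on all subjects in each group being evaluable; fewer evaluable subjects would raise them. The probabilities of zero rest on assumed response rates. The consequence is minor, and the case for changing the text is that the change is nearly free.

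**What to change.** In section 8.4.3.1, replace the conditional sentence with: *An exact (Clopper-Pearson) two-sided 95% CI will be reported for ORR and DCR, by dose level and overall, whatever the number of responses, including zero, with the denominator shown.*

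Optional: because 8.3 restricts response to re-evaluated patients while 8.4.3 refers to treated subjects, also report ORR among all treated subjects with measurable disease at baseline, counting those not re-evaluated as non-responders.

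The cost is SAP wording only, with no added data, visits or subjects. Intervals for single dose levels will be wide, and the optional ORR may be slightly lower than the one on the 8.3 set.
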